2.2 Analysis sets

The following analysis populations will be defined for statistical analysis.

- All patients: all patients who signed informed consent and entered in the study, including screen failure.
- Full Analysis Set (FAS): all enrolled patients (i.e. patients entered at week 0 visit 3).
- Safety: all enrolled patients included in the FAS population who were given at least one dose of study drug.
- Intent-to-treat (ITT): all patients included in the safety population with at least one post-baseline efficacy assessment and with the Cw6 assessment.
- Per-Protocol (PP): all patients included in the ITT population who completed the study without any major protocol violation.
- Core phase completers set: All patients who completed the Core phase visits (Week 24) are called core phase completer set.

The primary and secondary objectives will be evaluated on the ITT population. A supportive analysis will be done on the PP population.

All safety evaluations will be based on the safety set.

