2.5.2 Statistical hypothesis, model, and method of analysis

The proportion of patients who reach PASI 90 at 16 weeks will be presented with the one-tailed 97.5% confidence interval of the Cw6 positive (POS) – Cw6 negative (NEG) difference.

The null hypothesis:

H0: Cw6 POS - Cw6 NEG \ge 0.12: The difference in proportion of patients achieving PASI 90 response between the Cw6-positive cohort (Cw6 POS) and the Cw6-negative cohort (Cw6 NEG) is at least 12%.

The alternative hypothesis:

HA: Cw6 POS - Cw6 NEG < 0.12: The difference in the proportion of patients achieving PASI 90 response between the Cw6-positive cohort (Cw6 POS) and the Cw6-negative cohort (Cw6 NEG) is less than 12%.

The proportion of PASI 90 response by cohort as well as the difference between cohort together with 97.5% upper CI will be provided using Clopper Pearson CI method.

A logistic regression analysis model will also be fitted, considering age, geographical region (i.e. north vs south vs central), BMI categories (<25 vs >=25), waist circumference, smoking status (Yes vs No), metabolic syndrome (yes vs no), previous PsO therapy (naïve vs previous systemic therapy vs previous biologic therapy), PsA (yes vs no), age at diagnosis of psoriasis, TNF α -308 polymorphism, IGA mod 2011 (severe, moderate, mild) as strata factors.

Model selection:

If model does not converge due to particular covariate(/s), the corresponding covariate(/s) will be removed from the model using Stepwise selection method until model get converged.

Interpretation:

We can conclude that PASI 90 response in the Cw6-negative cohort is not less than 12% with respect to the Cw6-positive cohort if the upper bound of the 97.5 % CI of the difference (Cw6 POS - Cw6 NEG) is less than the non-inferiority margin of 12%.

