2.5.3 Handling of missing values/censoring/discontinuations

For patients who prematurely discontinue the study for any reason or patients with missing visits (after baseline), PASI will be imputed using the Last Observation Carried Forward (LOCF) approach. Additionaly non-responder imputation (NRI) analysis will be performed on primary endpoint (i.e., PASI 90 response with logistic regression analysis).

Non-responder imputation rule:

Non-responder imputation will be used: Missing values with respect to response variables based on PASI score will be imputed with non-response regardless to the reason for missing data (e.g. premature study discontinuation, missed visit, administrative issues), exceptions will apply to the following:

• If a subject dropped out the study prior to last scheduled visit and being responders consecutively at least for two preceding visits, the subject will be imputed as responder for the last scheduled visit.

• If a subject who was responder at visit x-1 and visit x+1 but has missing data at visit x, then the subject will be imputed for visit x.

The approach describes above will be adopted also for PASI 90 assessement reported in the extension phase.

The LOCF approach, as well as the NRI approach will be performed for drop-outs and patients with missing visits in between, however no imputation will be done on any visits for patients – entered in the extension phase **and** who have completed the study before reaching 72 weeks.

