2.5.4 Supportive analyses

A sensitivity analysis on the primary efficacy variable will be performed considering the patients who prematurely discontinued the study without a 16-week PASI assessment as non-responders. Hence, for this analysis non-responders patients are those who are PASI 90 responders who prematurely discontinued the study without a 16-week PASI assessment.

Summary of the number and percentage (n and %) of responders patients at week 16 will be presented by cohorts for this supportive analysis. Clopper Pearson confidence interval for a proportion will also be provided.

This supportive analysis will be done on the ITT set.

A supportive analysis on the primary efficacy variable will be also provided using prevalence approach (observed data) on ITT set and also using the PP set using both LOCF and NRI imputation method as well as prevalence approach.

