2.7.2 Statistical hypothesis, model, and method of analysis

PASI

Summary statistics for PASI 50, PASI 75, PASI 90, PASI 100 response by visit will be presented with absolute and relative frequencies. Confidence intervals for response rates will be derived as well, based on the score method including continuity correction (Newcombe 1998). The summaries will be done using prevalence (observed data), LOCF and NRI approaches.

Summary statistics will be provided for absolute PASI scores and for percent changes from baseline by visit and cohort using prevalence, and LOCF approches. Graphical representations will also be provided on ITT set.

The two cohorts will be compared on PASI scores (absolute change from baseline) using MRMM model with LOCF, prevalence and MI approaches on ITT set.

PASI Changes vs baseline: Linear Mixed Model for Repeated Mesurements (MMRM):

In order to evaluate if there is a differences between cohorts in PASI changes at each time point vs week 0, a longitudinal analyses of changes from baseline will be performed over the course of the study including all the measurements assessed at each time point for the ITT population using a linear mixed model for repeated measurements (MMRM). An unstructured

covariance matrix for the repeated measures within each patient will be applied in the analysis, if the model does not converge, compound symmetry will be used. The explanatory variables in the longitudinal model include cohort, visit, cohort-by-visit interaction, missing data pattern (completers, missing one assessments, missing two assessments, missing three assessments, etc till all visits in the overall study period), propensity score, and corresponding baseline (week 0). The two cohorts will be compared at each time point by reporting a point estimate, p-value, and 95% confidence interval for the treatment difference, based on least squares means.

The propensity score analysis will consider the following baseline factors: age, geographical region (i.e. north vs south vs central), BMI categories (<25 vs >=25), waist circumference, smoking status (Yes vs No), metabolic syndrome (yes vs no), previous PsO therapy (naïve vs previous systemic therapy vs previous biologic therapy), PsA (yes vs no), age at diagnosis of psoriasis, IGA mod 2011 (severe, moderate, mild) as strata factors. This approach allows us also to maximize the analysis model adding only one variable instead of several ones.

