5.4.3 Secondary analysis

The SAS procedure PROC FREQ with Method= NEWCOMBE option, will be used to derive Confidence intervals for response rates with the following sample SAS code:

PROC FREQ DATA = \dots ;

BY visit;

TABLES trtan*resp / riskdiff (column=2 cl=(NEWCOMBE));

RUN;

The SAS procedure PROC MIXED will be used for linear mixed model for repeated measurements (MMRM) analysis with the following sample SAS code:

PROC MIXED DATA=dataset noclprint;

CLASS cohort vis1n usubjid MissingPattern;

MODEL Changes= cohort week0 dropout visit prop_score

cohort*visit cohort*MissingPattern;

REPEATED visit/subject=usubjid TYPE=cs;

LSMEANS cohort*visit/pdiff cl;

RUN;

The SAS procedure PROC PHREG, will be used to perform computed using a stratified Cox proportional hazards regression model with Cw6 group and baseline PASI as explanatory variable with the following sample SAS code:

PROC PHREG DATA=....;

CLASS trtpn baseline ..;

MODEL var*censor(0)= trtpn base.../rl ties=efron ;

RUN;

The SAS procedure PROC LIFETEST, will be used to perform log-rank test and to plot Kaplan-Meier estimates of the cumulative rate for each cohort with the following sample SAS code:

PROC LIFETEST DATA=... PLOT;

TIME timevar*censor(0);

STRATA ...;

RUN;

The SAS procedure PROC CORR, will be used to perform Spearman's (or Pearson's product moment correlation depending on data distribution) correlation with the following sample SAS code:

PROC CORR DATA = pearson/spearman OUTP=CORR;

VAR VAR1 VAR2;

RUN;

The SAS procedure PROC UNIVARIATE with NORMAL option, will be used to check the normality with the following sample SAS code:

PROC UNIVARIATE DATA = normal;

VAR var.../options...;

CLASS var;

RUN;

The SAS procedure PROC UNIVARIATE, will be used to perform Wilcoxon signed rank test with the following sample SAS code:

PROC UNIVARIATE DATA =;

VAR var...;

RUN;

The SAS procedure PROC TTEST, will be used to perform paired t-test with the following sample SAS code:

PROC TTEST;

PAIRED VARbefore*VARafter;

RUN;

The SAS procedure PROC FREQ with EXACT statement equal to MCNEM or AGREE will be used to perform Mc Nemar's test with the following sample SAS code:

PROC FREQ DATA =;

TABLES trtan*resp;

EXACT MCNEM or AGREE;

RUN;

SAS code for poisson regression model

proc genmod data=demo_ae ;

class cw6 sex age_group/ param = glm;

model numev = cw6 age_group sex / type3 dist=poisson;

lsmeans cw6 /ilink cl diff;

lsmeans age_group /ilink cl diff;

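### The per-protocol exclusion list omits two concomitant-drug codes, the exclusion tables conflict with the ITT definition, and no planned run counts a week-16 PASI 90 reached after other psoriasis treatment as failure

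*SAP*

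**What the plan says.** **Missing-data rules.** SAP 2.5.3 uses LOCF for the primary analysis and adds a second approach: "non-responder imputation (NRI) analysis will be performed on primary endpoint (i.e., PASI 90 response with logistic regression analysis"). Both act on absent data: "The LOCF approach, as well as the NRI approach will be performed for drop-outs and patients with missing visits in between". The extra sensitivity analysis in 2.5.4 concerns patients who "prematurely discontinued the study without a 16-week PASI assessment as non-responders". SAP 2.5.4 also plans an observed-data run on ITT, and runs "also using the PP set using both LOCF and NRI imputation method as well as prevalence approach".

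**Analysis set and decision.** ITT in SAP 2.2 is "all patients included in the safety population with at least one post-baseline efficacy assessment and with the Cw6 assessment", with no condition on other drugs taken. Under 2.5.2 the claim is made if the upper limit of the POS − NEG difference "is less than the non-inferiority margin of 12" percent.

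**Other treatment.** Protocol 5.5.6 leaves medication to clinical need. Protocol 5.5.8 bans the Table 5-1 treatments after screening but lets a user stop the banned drug and stay in the study. Protocol 5.5.9 lists prohibited use as a reason to stop secukinumab. Protocol Section 6 asks patients off secukinumab to return for the same visits. SAP 2.4.2 defines rescue by three products and three reasons and tabulates it; SAP 2.11 costs rescue under a different description (methotrexate, corticosteroids). No efficacy section uses either.

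**Exclusion tables.** The note in SAP 2.3 lists the codes for concomitant psoriasis medication, among them COMD10 and COMD12. Neither is in the major-deviation list of the same section or in 5.5 Table 1.

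**The concern.** The study compares two genotype cohorts that were not randomised, and the claim rests on one confidence limit. If some week-16 responses were reached with the help of another psoriasis drug, and if that help differed between cohorts, the limit moves. An excess in Cw6-negative patients favours the claim, an excess in Cw6-positive patients works against it, and equal rates leave the difference unchanged. A reader who wants to know whether the conclusion holds for secukinumab without such help would look to the supportive analyses. None answers that question directly.

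The per-protocol set is the nearest thing to an answer, which is why errors in its exclusion list matter. As listed, it can retain patients whom the SAP itself describes as taking psoriasis medication during the study.

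**Working it through.** **1. What each planned run does with a week-16 score observed after other treatment.**

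| Run | What triggers a change | Effect on such a score |
|---|---|---|
| ITT, LOCF | left the study, or missing visit | used as recorded |
| ITT, NRI | missing value | used as recorded |
| ITT, 2.5.4 sensitivity | left without a week-16 PASI | used as recorded |
| ITT, observed data | none | used as recorded |
| PP, all three | listed deviation, or did not complete | patient removed, not failed |

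The ITT entries follow from the absence of any rule; the SAP does not say this in words. Such scores can arise under Protocol 5.5.8 (patient stays) or 5.5.9 (secukinumab stopped), because Section 6 brings the patient back for PASI either way.

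**2. The exclusion tables, side by side.**
- SAP 2.3 note, concomitant use: COMD02, 04, 06, 08, **10**, **12**, 14, 17, 18, 19.
- Of these, in the 2.3 major-deviation list and 5.5 Table 1: COMD02, 04, 06, 08, 14, 17, 18, 19.
- COMD09 and COMD11 are prior infliximab and golimumab, so by the numbering pattern COMD10 and COMD12 are probably the same drugs taken concomitantly. As written, such a patient stays in PP unless another rule, such as non-completion, applies.
- Table 1 gives the prohibited-drug deviations code 4 and excludes them from PP only. Table 2 prints code 4 in what appears to be the ITT row, which would remove them from ITT as well. One source of the clash is visible: the Table 1 row for no valid PASI after baseline also carries code 4 and does exclude from ITT.

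**3. The design figure.** Inputs from SAP Section 3: one-sided alpha 0.025, power 80%, 80% response in Cw6-positive, margin 0.12, 219:146. The Cw6-negative rate is not stated; I assume 80%.

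n(POS) = (1.960 + 0.842)² × [0.16 + 0.16 × 219/146] / 0.12² = 218.02, rounded up to 219. This gives 146 Cw6-negative and 365 in total, as stated, with power 80.2%.

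**4. How many reclassified responders would matter.** The documents give no rescue counts, so this shows sensitivity only. The difference shifts by r_NEG/146 − r_POS/219, where r is the number of responders affected. Three Cw6-negative only: 2.1 points wider. Two Cw6-negative and three Cw6-positive: 0. Three Cw6-positive only: 1.4 points narrower.

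Upper limits start from 80% in each cohort and reclassify Cw6-negative responders only. Wald is d + 1.96 × SE (unpooled); Newcombe is without continuity correction. SAP 2.2 needs only one post-baseline assessment, so ITT could approach the 406 enrolled; I assume 243/163 for that case.

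| Reclassified | 175/219 v 117/146: Wald, Newcombe | 194/243 v 130/163: Wald, Newcombe |
|---|---|---|
| 0 | 8.14, 8.41 | 8.05, 8.29 |
| 5 | 11.87, 12.07 | 11.37, 11.55 |
| 6 | 12.61, 12.80 | 12.03, 12.20 |

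The limit passes 12 points at six by Wald in both cases. By Newcombe it takes five at 219/146 and six at 243/163. If three Cw6-positive responders are also reclassified at 219/146, seven Cw6-negative are needed by Wald (12.05).

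**5. Error rate against a secukinumab-only target.** With true rates of 80% v 68% at 219/146, the chance of concluding non-inferiority is Φ((0.12 − d)/SE − 1.96). One, two or three extra points in Cw6-negative give 4.0%, 6.3% and 9.5% instead of 2.5%. The same extra points in Cw6-positive give 1.5%, 0.8% and 0.5%.

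**The case against.** The strongest reply is that the target is already defined. SAP 2.5.2 states the hypothesis as a difference in the proportion reaching PASI 90 in the analysed cohorts, with no condition on other drugs. Using observed scores whatever else was taken is ordinary ITT practice. That stands. A reader might infer from the figures in step 5 that the planned test has inflated type I error. The documents do not support this: those figures hold only against a secukinumab-only hypothesis that the SAP does not state, and against the written hypothesis there is no inflation from this source.

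Second, the per-protocol runs catch much of this. Methylprednisolone, acitretin and possibly the steroid cream in SAP 2.4.2 plausibly fall under COMD17, COMD18 and COMD19. That stands too, but PP removes these patients along with non-completers and eligibility violators, so a difference between PP and ITT cannot be traced to other treatment.

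Third, cases look rare. The rescue list in a 72-week plan is short, and patients rescued for worsening psoriasis are unlikely PASI 90 responders. Infliximab or golimumab alongside secukinumab is improbable, so the COMD10 and COMD12 omission may affect nobody. This limits the size of the problem; it does not make the tables agree.

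Fourth, part of the output may already exist. SAP 2.7.2 says "The summaries will be done using prevalence (observed data), LOCF and NRI approaches", and the code in 5.4.3, "TABLES trtan*resp / riskdiff (column=2 cl=(NEWCOMBE", would print an interval for the cohort difference. But those NRI results still respond only to missing data, and the SAP does not set them against 12 points.

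Finally, a crude composite rule could mislead: one early use of a topical should not turn a secukinumab responder into a failure. The trigger must be narrow.

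**Conclusion.** Two points are wrong as written: COMD10 and COMD12 are missing from the major-deviation list and Table 1, and Table 2 appears to contradict the ITT definition. Both are plain inconsistencies, whatever one thinks of the estimand.

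The rest is a cheap improvement and not an error. Taking ITT as in SAP 2.2, no planned analysis counts a week-16 PASI 90 after other psoriasis treatment as failure. If Table 2 were followed literally, users of listed prohibited drugs would be dropped from ITT, still not failed.

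A reader might conclude that the primary result is biased towards non-inferiority, or that rescue could readily reverse it. Neither follows. The direction is unknown, the documents give no counts, and reversal from the design expectation needs five or six Cw6-negative responders with none in Cw6-positive. These numbers rest on 80% response in both cohorts and on 219/146 or an assumed 243/163.

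**What to change.** **Corrections.** Add COMD10 and COMD12 to the major-deviation list in SAP 2.3 and to 5.5 Table 1, as exclusions from PP. Remove code 4 from the apparent ITT row of Table 2, and give the row for no valid post-baseline PASI its own ITT-excluding code.

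**Addition to SAP 2.5.4.** Keep LOCF primary. Add one supportive NRI run on ITT in which week-16 PASI 90 is set to non-response if, after the first dose and before the week-16 PASI, the patient started a systemic, biologic or phototherapy psoriasis treatment from Protocol Table 5-1, or rescue as defined in SAP 2.4.2. Prohibited topicals count only if used within their Table 5-1 washout before the week-16 visit; I would apply the same limit to the steroid cream in 2.4.2. Because SAP 5.1.2 can place a partial start date just after first dose, show the result with and without imputed dates. Report the number reclassified per cohort, and the POS − NEG difference with its 97.5% upper limit beside 12 points.

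**Cost.** SAP wording, one derived flag and one table from data already collected. The primary result and patient care do not change. The added run has lower power. At 219/146 it goes from 80.2% to 78.7%, 77.4% or 76.1% if 1, 2 or 3 points are reclassified in both cohorts, and to 72%, 63% or 53% if in Cw6-negative only. At 243/163 the starting point is 84.2%, and the Cw6-negative-only values are 76.6%, 67.6% and 57.7%. A missed limit in this run is something to explain; it does not overturn the primary conclusion.

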2.5.4 Supportive analyses

A sensitivity analysis on the primary efficacy variable will be performed considering the patients who prematurely discontinued the study without a 16-week PASI assessment as non-responders. Hence, for this analysis non-responders patients are those who are PASI 90 responders who prematurely discontinued the study without a 16-week PASI assessment.

Summary of the number and percentage (n and %) of responders patients at week 16 will be presented by cohorts for this supportive analysis. Clopper Pearson confidence interval for a proportion will also be provided.

This supportive analysis will be done on the ITT set.

A supportive analysis on the primary efficacy variable will be also provided using prevalence approach (observed data) on ITT set and also using the PP set using both LOCF and NRI imputation method as well as prevalence approach.

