A recently published paper demonstrated an association between the presence of the HLA-C*06 allele and the response to ustekinumab. The study showed an increased response to ustekinumab in Cw6-positive (Cw6POS) patients [PASI 75 at week 12: 96.4% in Cw6POS vs. 65.2% in Cw6-negative (Cw6NEG) patients; P = 0.008] and that HLA-Cw6POS patients

also responded faster to ustekinumab, 89.3% of them reaching PASI 50 at week 4, after a single injection (vs. 60.9% of HLA-Cw6NEG patients). The superior response of HLA-Cw6POS patients was maintained throughout the study period and reached the highest statistical significance for PASI 75 at week 28 (96.35% Cw6POS vs. 72.7% Cw6NEG; odds ratio 9.8). Analysis of TNFAIP3 rs610604 polymorphism and LCE3B/3C gene deletions did not show any significant association with response to ustekinumab (Talamonti M et al. 2013).

Secukinumab is a high-affinity human monoclonal anti-human IL-17A antibody of the IgG1/ κ isotype that demonstrated a favorable safety and tolerability profile with robust clinical activity in a series of Phase II studies, and is undergoing an extensive Phase III program (Gisoni P et al 2014). Secukinumab binds to human IL-17A and neutralizes its bioactivity by inhibiting IL17A produced by both Th17 cells and cells of the innate immune system, thus providing complete anti IL17A blockage. Targeting IL-17A has the potential to reduce autoimmune inflammation while leaving other immune functions undisturbed. While targeting of Th1-promoting or Th17-promoting cytokines affects critical mediators such as IFN- γ , IL-22 and IL-21, selective targeting of IL-17A leaves these Th1/17 activities, as well as certain protective functions of innate cells intact (Patel DD et al. 2013). Furthermore, as a fully human monoclonal antibody, secukinumab has low immunogenicity (i.e., antidrug antibodies) compared to current or emerging biologic therapies that are not fully human. Data linking secukinumab efficacy to a particular genetic biomarker are lacking. However, due to its mechanism of action, the efficacy of secukinumab should not be HLA restricted, and when considering the main haplotype associated with psoriasis, no difference between Cw6-negative and positive patients is expected.

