2.14 Interim analysis

No interim analysis is planned for this study.

3 Sample size calculation

The primary objective of this study is to evaluate the clinical response in PASI 90 at week 16 of Cw6-negative and Cw6-positive psoriatic patients. According to literature data, Cw6-positive patients will be about 60% of the entire psoriatic patient population.

From a previous study with ustekinumab (Talamonti et al. 2013) we can observe a difference in response to PASI 90 between Cw6-positive vs Cw6-negative patients of around 30%, in favor of Cw6-POS. Therefore, it is sensible to expect a response in the Cw6-negative cohort not less than 12 % respect to the Cw6-positive group. Further considerations are stated in the paragraph below.

Phase III data on secukinumab show a PASI 90 response at 16 weeks of 71%. Under the assumption that 60% of all the enrolled patient population is represented by Cw6-POS patients, we can reasonably assume to observe a proportion of patients with PASI 90 of 80% in the Cw6-POS cohort.

Under these assumptions, considering a one-side alpha level of 0.025 and a power of 80%, 365 patients (219 Cw6-POS and 146 Cw6-NEG) are sufficient to evaluate if the response in terms of PASI 90 in the Cw6-negative cohort is not less than 12% respect to the Cw6-positive cohort.

Considering a dropout rate at 16 weeks of 10% equally divided in the two studied cohorts, a total of 406 patients should be enrolled.

All calculations were done with NQuery 7.0.

A power analysis based on a different Cw6 patient distribution was made in order to facilitate patient enrollment without power-loss in the primary endpoint evaluation. Table 3-1 shows how the enrollment rate should be set free until the ratio between Cw6-POS and Cw6-NEG reaches the 1:1 rate-distribution, with a power of at least 80%.

In particular, the number of Cw6-POS evaluable patients will range from 219 to 182, whereas those in the Cw6-NEG cohort will range from 146 to 182.

Based on the table below, the enrollment in one of the two cohorts will be stopped when the target number is achieved (a maximum of 244 Cw6-POS patients will be allowed).

Table 3-1:Power analysis

Power	Ratio	Cw6	Cw6	Cw6	Cw6	Overall	Cw6	Cw6	

For business use only

		POS	POS	POS	POS		POS	POS
		%	%	Ν	Ν	Ν	%	%
80%	0.66	60%	40%	219	146	365	244	163
80%	0.70	59%	41%	215	150	365	239	167
80%	0.72	58%	42%	212	153	365	236	170
80%	0.75	57%	43%	209	156	365	233	174
81%	0.79	56%	44%	204	161	365	227	179

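### The week-16 dropout-as-non-responder analysis is not specified on the scale of the 12-point margin, and its definition of a non-responder contradicts itself

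*SAP*

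**What the plan says.** **Decision rule.** SAP 2.5.2 allows the claim for the Cw6-negative cohort if the upper bound of the 97.5% interval for the difference (POS − NEG) "is less than the non-inferiority margin of 12" per cent.

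**Primary handling of missing data.** Protocol 9.4.3 and SAP 2.5.3 impute PASI by LOCF, both for patients who discontinue and for missed visits.

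**Strict sensitivity analysis.** Protocol 9.4.4 and the first sentence of SAP 2.5.4 treat patients who discontinued without a week-16 PASI as non-responders. The protocol names no output. SAP 2.5.4 does: "Summary of the number and percentage (n and %) of responders patients at week 16 will be presented by cohorts", followed by a Clopper-Pearson interval for a proportion.

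**Definition.** The second sentence of SAP 2.5.4, which begins with *Hence*, says that "non-responders patients are those who are PASI 90 responders who prematurely discontinued the study without a 16-week PASI assessment".

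**NRI.** SAP 2.5.3 adds non-responder imputation of the primary endpoint, specified as "i.e., PASI 90 response with logistic regression analysis". This rule has two exceptions under which a patient with a missing value is still counted as a responder.

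**Other supportive runs.** The end of 2.5.4 lists an observed-data analysis on the ITT set and LOCF, NRI and observed-data analyses on the PP set. It states no output for any of them.

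**The concern.** A sensitivity analysis of a non-inferiority claim has to answer one question: does the upper limit stay below the margin when missing outcomes are handled less favourably? The output named in 2.5.4 is two separate percentages, each with its own interval. The output named in 2.5.3 is an odds ratio. Neither is the quantity on which the claim rests.

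LOCF can carry a PASI 90 response forward for someone who left the study. If dropout differs between cohorts, LOCF and the strict rule can give different differences, and the report should show whether the conclusion changes.

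The definition adds a second problem. A programmer who followed the *Hence* sentence literally would count as non-responders only those PASI 90 responders who dropped out. Patients seen at week 16 without PASI 90 would be left out.

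**Working it through.** **1. The plan's own figure.** SAP section 3 states: "considering a one-side alpha level of 0.025 and a power of 80%, 365 patients (219 Cw6-POS and 146 Cw6-NEG) are sufficient". Inputs:
- POS rate 80%: "we can reasonably assume to observe a proportion of patients with PASI 90 of 80% in the Cw6-POS cohort".
- NEG rate: not given as a figure. I take 80%, because protocol 1.1 says "no difference between Cw6-negative and positive patients is expected".
- Margin 0.12, one-sided alpha 0.025, power 80%, allocation 219:146.

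n(POS) = (1.960 + 0.842)² × [0.8×0.2 + 0.8×0.2×(219/146)] / 0.12² = 7.849 × 0.40 / 0.0144 = 218.03, rounded up to 219. NEG is then 146 and the total 365. Power at 219/146 is 80.2%.

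For dropout: "Considering a dropout rate at 16 weeks of 10% equally divided in the two studied cohorts, a total of 406 patients should be enrolled". 365/0.9 = 405.6, so 406. By cohort, 219/0.9 gives 244 and 146/0.9 gives 163. The sample size reproduces and is not in question.

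**2. What the strict analysis would show if reported as a difference.** Assumptions, none of them data: 244 POS and 163 NEG patients, all in the ITT set; 80% response among patients assessed at week 16; LOCF carrying forward 80% response among dropouts. The upper limit is d + 1.96 × √[p₁(1−p₁)/244 + p₂(1−p₂)/163]. This is the Wald form, in line with the z-test riskdiff code in SAP 5.4.1.

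| Handling | Dropout POS/NEG | Responders | Rates | Difference (points) | Upper limit (points) | Below 12? |
|---|---|---|---|---|---|---|
| LOCF | any row below | 195/244, 130/163 | 79.9%, 79.8% | 0.2 | 8.1 | yes |
| Dropouts fail | 10%/10% (24, 16) | 176, 118 | 72.1%, 72.4% | −0.3 | 8.6 | yes |
| Dropouts fail | 8%/13% (20, 21) | 179, 114 | 73.4%, 69.9% | 3.4 | 12.4 | no |
| Dropouts fail | 5%/10% (12, 16) | 186, 118 | 76.2%, 72.4% | 3.8 | 12.5 | no |
| Dropouts fail | 5%/15% (12, 24) | 186, 111 | 76.2%, 68.1% | 8.1 | 17.1 | no |

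For the 8%/13% row: SE = √(0.7336×0.2664/244 + 0.6994×0.3006/163) = 0.0457, and 0.0342 + 1.96×0.0457 = 0.124. A Newcombe limit without continuity correction gives 12.5, the same conclusion. Overall dropout in that row is 41/407, about 10%, as planned.

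**3. What the specified outputs would show in the 8%/13% case.** The per-cohort Clopper-Pearson intervals are 67.3–78.8% and 62.3–76.9%. They overlap, and nothing in them signals that the limit has crossed 12.

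An odds ratio cannot be read against the margin without a base rate. A 12-point difference is a crude odds ratio of (0.72/0.28)/(0.60/0.40) = 1.71 at a POS rate of 72%, 1.88 at 80% and 2.10 at 85%. The planned model is also covariate-adjusted.

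**4. A caution for interpretation.** With equal 10% dropout all counted as failures, both rates are 0.9 × 80% = 72%. The chance of meeting the margin at 244/163 is then Φ(0.12/0.0454 − 1.96) = 75%. A missed margin in this analysis can therefore come from lost precision as well as from a shifted difference, so the estimate should be shown with its limit.

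**5. The two sentences of 2.5.4 side by side.** The first makes every discontinued patient without a week-16 PASI a non-responder. The second restricts non-responders to PASI 90 responders among them. They agree only if the second is read as the recoding needed relative to LOCF, which it does not say.

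**The case against.** A reader might infer that the difference is never produced under any alternative missing-data rule. The documents do not support that. SAP 2.7.2 runs the by-visit PASI 90 summaries under observed data, LOCF and NRI, and the code in 5.4.3 requests a Newcombe risk-difference interval by visit. A week-16 difference under NRI would therefore appear in the output. It is not tied to the 12% margin, however, and its NRI rule keeps some patients with missing values as responders, so it does not replace the strict analysis.

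The per-cohort counts also determine the unadjusted difference and its limit; the table above was built from just such counts. The information is not lost. What the plan lacks is the pre-specified result and its comparison with 12%. That part of the objection stands and limits the severity.

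The observed-data and PP runs could be taken to inherit the method of 2.5.2, since no other is named. The PP set excludes patients who did not complete the study, so its LOCF and NRI runs hardly test dropout.

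A reader might also infer that the non-responder rule is reversed. The first sentence of 2.5.4 and protocol 9.4.4 state it correctly, and the *Hence* sentence can be read as moving carried-forward responders who dropped out into the non-responder group. It is self-contradictory and incomplete as written, but reversal is only one reading.

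Finally, the plan assumes dropout equal in the two cohorts, and in that case the illustrated conclusion does not change.

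**Conclusion.** The point holds as a gap in specification. The strict week-16 analysis is written to report single-cohort proportions, and NRI of the primary endpoint to report a logistic model. Neither is written to be judged against the 12-point margin that decides the trial. The *Hence* sentence needs correction.

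On size: under the stated assumptions, the strict upper limit is 8.6 points at the planned equal dropout and between 12.4 and 17.1 at the unequal splits tried, against 8.1 under LOCF. The documents give no differential dropout rate, so these figures show what the analysis should be able to detect and do not predict a result.

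A reader might go further and infer that the error rate of the primary test is inflated. The documents do not support that: it would require unequal dropout and dropout-as-failure as the target, and the proposed change leaves the LOCF primary analysis as it is. The change should be made, but the primary test does not depend on it.

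**What to change.** In SAP 2.5.4, replace the *Hence* sentence with: *Non-responders are patients observed without PASI 90 at week 16 plus all patients who prematurely discontinued without a week-16 PASI assessment, whatever their carried-forward status.* This keeps protocol 9.4.4's restriction to discontinued patients. Add that continuing patients who only missed the week-16 visit keep their status from the primary analysis.

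Then state that, for this analysis and for the NRI analysis in 2.5.3, POS − NEG will be reported with the same upper 97.5% limit and the same comparison with 12% as in 2.5.2. The per-cohort percentages and the logistic model can stay as additional output.

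The cost is one corrected sentence, one added sentence and a rerun of the riskdiff code already in 5.4.1 on two recoded response variables. No new data are needed, and neither the sample size nor the primary analysis changes.
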